3.4.3. Recruitment and identification of potential participants

Participants will be recruited using convenience sampling through websites, e-newsletters/blogs and

social media (Twitter, Facebook) via the researchers' affiliated professional accounts (e.g. Deakin

University, ACBRD). Australian diabetes charities, organisations and associations (e.g. Diabetes

Australia, Diabetes Victoria) will be notified of, and encouraged to promote, the study through

similar online means.

A participant prize draw will be used to incentivise participation and aid recruitment. All participants who complete the follow-up survey will be entered into a prize draw to win one double-pass gold class cinema voucher.

3.4.4. Consent

An online Plain Language Statement and Consent Form (PLSCF) will be developed, and will describe the purpose of the study to participants, the procedures to be followed, the risks and benefits of participation and contact details (email address and telephone number) for the research team in the event of any queries or questions. Prior to completing any study component (i.e. responding to screening questions to determine eligibility), potential participants will need to tick a box to confirm they have read and understood the PLSCF and consent to taking part. Consent will be voluntary and free from coercion. Participants will be encouraged to print a copy of the PLSCF for their records and a copy of the consent form will be accessible to all participants on the study website throughout their participation. The PLSCF and consent form will advise participants that they may be contacted via email and asked to respond to a small number of follow-up questions (via email reply or telephone) for safety reporting purposes (See Section 6.3.2). Participants will be advised that their non-response to these additional questions will not affect their eligibility or participation in this pilot study.

3.4.5. Participant withdrawal

Participants are free to withdraw from the study at any time upon their request, for any reason. Participants who *request* to be withdrawn from the study will be asked to nominate, but not required to provide, a reason for withdrawal. Withdrawing from the study will not affect their relationship with the researchers or study sponsors.

Participants will be withdrawn from the study if they do not submit a baseline survey, and therefore are not allocated to a trial arm. The investigator will also withdraw all participants from the study intervention if the study is terminated. Where applicable, basic de-identified sample characteristics (gender, age, diabetes duration), trial arm allocation, time of withdrawal (e.g. pre or post trial arm allocation) and reason for withdrawal, will be maintained for reporting purposes.

3.5. Trial allocation

3.5.1. Randomisation and blinding

After the baseline survey is submitted, participants will be allocated to one of two groups, on an equal allocation basis, stratified by gender. The randomisation sequence will be computer generated and the allocation fully concealed from the investigator, researcher team and participants.

Upon trial arm randomisation participants will receive an email specifying access details (including a unique log-in) to their allocated online resource about insulin therapy. Participants in both arms will be asked to explore their allocated resource within a 2-week period, and will receive one reminder email during this period encouraging them to access/log into the resource. Access to the online resource will conclude following the 2-week period, at which time participants will be requested (via email) to complete the follow-up survey.

3.5.2. Intervention group

Intervention group participants will receive access to the novel psycho-educational website. The development process (Stage 1) of intervention content and design is described in the Stage 1 Protocol. A description of the intervention to be assessed in the Pilot Study (Stage 2) will be added to the protocol as an appendix prior to study commencement.

3.5.3. Control group

Control arm participants will be directed to a static webpage including links to publications about insulin therapy which are currently available online to Australians with T2D. Specifically, the website will include text-based factsheets about insulin and other T2D medications published by the National Diabetes Services Scheme (NDSS): "Medication for type 2 diabetes", "Insulin and type 2 diabetes".

3.6. Study procedure

Following provision of informed consent, participants will be asked to complete eligibility screening questions online. Eligibility will be automatically determined based on responses and ineligible participants will be thanked for their interest in the study. Eligible participants will be directed to complete an online baseline survey. Following submission of the survey, participants will be randomised to a study arm and receive relevant resource access details via an automated email.

Participants will be able to access the relevant resource at their leisure within a 2-week period. One week following allocation participants will receive an automatically generated reminder email to access/log into the resource. Following the 2-week period, participants will be sent an automated email with a link to the follow-up online survey. The follow-up survey will be available for completion for two weeks. Participants who have not completed the survey within one week of receipt will be sent reminder email. Participation (from eligibility screening to end-of study) will involve a minimum of two weeks and maximum of four weeks. Study endpoint for all participants will be marked by either submission of the follow-up survey (within 14 days of request), or non-submission at 15 days following survey request. The study procedure is detailed in Figure 1. A and the timeline for the entire study protocol is detailed in Section 7.

[figure not shown]

Figure 1. Flow chart of Stage 2: Pilot study procedure.

3.6.1. Schedule of data collection

Table 1 details the self-reported demographic, clinical, psychosocial, and study-specific resource acceptability and experience data to be collected and the time-points at which they are to be collected.

Table 1. Details and timing of participant data collection

Concepts	Variables or Measures	Eligibility screening	Baseline survey	Follow- up survey
About you				-
Contact information	First name*, email address*		Х	
	Age*, gender*, country of residence*	Χ		
	Country of birth, primary language,			
Demographics	relationship status, employment status,		Х	
	qualifications, postcode (indicator of socio-		^	
	economic status)			
Country of birth, primary language, relationship status, employment status, qualifications, postcode (indicator of socio- economic status) Clinical characteristics Type of diabetes*, diabetes duration*, current diabetes management regimen*, prior use of self-administered injectable treatment* Diabetes Brand names of currently administered diabetes medications, most recent HbA1c (if known), frequency of self-monitoring of glucose (if any), diabetes-related complications General health Co-morbidities, weight and height Recall of discussion/education about to insulin therapy in clinical setting: prior				
	current diabetes management regimen*, prior use of self-administered injectable	Х		
Diabetes	diabetes medications, most recent HbA1c (if known), frequency of self-monitoring of glucose (if any), diabetes-related		Х	
General health	Co-morbidities, weight and height		Х	
Clinical discussion of insulin therapy	·		Х	
Psychosocial char	acteristics			
Psychological insulin receptiveness	Hypothetical willingness to commence insulin (41)*	Х		Х
Attitudes towards insulin	Insulin Treatment Appraisal Scale: ITAS (39)		Х	Х
Diabetes-specific knowledge	Michigan Diabetes Research and Training Center's Revised Diabetes Knowledge Test: DKT-R (42)		Х	Х

Study Name: Development, Feasibility, and Efficacy of a Web-Based Intervention to Reduce Psychological Barriers to Insulin Therapy among Adults with Type 2 Diabetes

Protocol Number: SA-2017-11697; Version & date: version 2.2b (stage 2 only), dated 6 June 2019

Concepts	Variables or Measures	Eligibility screening	Baseline survey	Follov up surve		
Diabetes-specific distress	Problem Areas In Diabetes: PAID (43)		Х	Х		
Illness	Brief Illness Perceptions Questionnaire:		Х	Х		
perceptions	BIPQ (44)		^	^		
Diabetes-specific	Confidence In (type 2) Diabetes Self-		Х	Х		
self-efficacy	management scale: CIDS-2 (45)		Λ	Λ		
	Access to online resources during two-week					
	period (yes/no)					
	If no:					
	Reasons for not accessing (pre-					
	defined response options and/or					
	free-response answers available)					
	If yes:					
	User rating of resource: ease of					
Resource	use; understanding and relevance					
	of content; acceptability of design,			Χ		
self-efficacy mana Acces perio If no:	length, and online format					
	Preference for alternative					
	information sources (e.g. hard copy					
	leaflet, clinical education)					
	Willingness to recommend the					
	resource to others					
	Likes/dislikes about the resource					
	How the resource could be					
	improved					
Further	Free-text box for participant to provide any			Х		
comments	further feedback.					

^{*}Question completion required for participation. ^ study-specific items to be developed.

3.6.2. Protocol compliance and loss to follow-up

Accurate records will be kept regarding participant online resource access, if and when surveys are submitted and how complete they are. To improve participant retention and protocol compliance, trial participants will receive two reminder emails or text messages: 1) to access/view the allocated online resource, sent one week following allocation, and; 2) to complete the follow-up online survey, sent one week after survey completion is requested (only for participants who have not yet submitted the online survey). All participants will be asked to complete the follow-up survey, regardless of compliance with the protocol in the form of accessing the allocated online resource.

Participants who do not complete a follow-up survey within two-weeks of receipt will be declared 'lost to follow-up'. Data collected from participants declared lost to follow-up will be maintained for analysis.

3.6.2.1. Replacements

Recruitment will be ongoing until 40 consenting eligible participants are allocated to a trial arm. A 50% attrition rate is incorporated into our estimated sample size and replacements will not be made for losses to follow-up.

3.7. Outcomes

This pilot study is not designed or powered to test for statistically significant impact and therefore we do not specify a primary outcome, or set a level of statistical significance for interpreting analyses. The following outcomes reflect the defined primary and secondary study objectives.

1. Feasibility assessment outcomes:

- a) Recruitment ease: Time (days) taken to recruit and enrol (trial arm allocation) 40 consenting eligible participants; proportion (%) of eligible participants who submit a baseline survey (are enrolled/allocated);
- b) Protocol compliance: Proportion (%) of 'enrolled' participants who access the allocated resource ≥1 time(s).
- c) Loss to follow-up: Proportion (%) of enrolled participants who do not submit a follow-up survey
- d) Data completeness: proportion (%) of participants with complete baseline survey data; proportion (%) of participants with complete follow-up survey data

2. Acceptability assessment outcomes:

- a) Website analytics: average number of online resource visits; time (minutes) spent on online resource; most commonly (frequency, %) viewed pages (intervention only)
- b) Quantitative survey feedback: frequency (%) of participants who agree with positively worded study-specific items, comparing intervention/control online resources;
- c) Qualitative feedback: common themes identified for participants likes and dislikes about the resources and how they could be improved.
- 3. Likely effect of the intervention assessment outcome:

a) Mean change in Insulin Treatment Appraisal Scale (ITAS) Negative scores from baseline to follow-up survey, compared to the control arm.

3.8. Data management

3.8.1. Data collection

All participant-reported data will be collected online via QualtricsTM, hosted through the Deakin University secure network. Once consent is provided, eligibility screening and baseline survey data will be collected in a single sitting. An email will be sent to the participant with a unique link to the follow-up survey following the trial.

The study website will require participant log-in, allowing for collection of website usage data for each participant, including hits, page views (frequency / duration), visit sessions (frequency / duration), click path.

3.8.2. Data storage

During the active study period, participant content and survey data will stored in Qualtrics™ via the Deakin University secure network. Only the research team will have access to this password-protected Qualtrics account. At the conclusion of the study all Qualtrics data and website usage data will be downloaded and linked according to participant ID. De-identified quantitative participant data will be saved as an IBM SPSS file and responses to free-text questions will be stored in an excel spreadsheet (which allows for a greater number of characters for string variables). Identifiable information (email, name) with linking participant ID will be separated from study data and stored in a password-encrypted excel spreadsheet. Safety follow-up interview data will be stored electronically (i.e. audio files). All data will be stored in a secure Deakin University computer file accessible only by the ACBRD research team. In accordance with clinical trial regulations, all original data will be kept for a minimum of 15 years following the publication of results and then disposed of by erasing of electronic files.

Study data collected from withdrawn participants will be deleted, with the exception of basic deidentified sample characteristics (gender, age, diabetes duration), trial arm allocation, time of withdrawal (e.g. pre or post trial arm allocation) and reason for withdrawal, where applicable.

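### Deleting the data of randomised participants who ask to withdraw leaves protocol compliance and baseline completeness unknown for them

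*Protocol*

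**What the plan says.** **Deletion.** Protocol 3.8.2: "Study data collected from withdrawn participants will be deleted". The exceptions are three characteristics (gender, age and diabetes duration) and "trial arm allocation, time of withdrawal (e.g. pre or post trial arm allocation) and reason for withdrawal, where applicable". Section 3.4.5 gives the same list. Website access, baseline survey answers and survey completeness are not on it.

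**Who is withdrawn.** Section 3.4.5 has two routes that matter here. One is by request: "Participants are free to withdraw from the study at any time upon their request, for any reason". The other is administrative: "Participants will be withdrawn from the study if they do not submit a baseline survey, and therefore are not allocated to a trial arm". Only the first can involve someone who has been randomised.

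**Silent drop-outs.** Section 3.6.2 treats people who do not return the follow-up survey differently: "Data collected from participants declared lost to follow-up will be maintained for analysis". The same section promises accurate records of resource access, survey submission and survey completeness.

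**Outcomes.** In section 3.7, compliance (1b) is the percentage of enrolled participants who open their allocated resource at least once, and 1a equates enrolment with allocation to an arm. Loss to follow-up (1c) is also a percentage of those enrolled. Data completeness (1d) is a percentage of participants, not explicitly of those enrolled, at baseline and at follow-up.

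**Use.** Section 3.2.1 names protocol compliance within the primary objective. Section 3.9.1 says that compliance, completeness and loss to follow-up will inform the sample size of the main trial.

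**The concern.** If the deletion rule is followed exactly, it erases the fields that two feasibility outcomes need, for people who belong in the enrolled group. Compliance is part of the primary objective and an input to planning the main trial. An analysis plan can say how to count people whose status is unknown, but it cannot restore their access records.

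The rule also applies by default. It does not separate a participant who merely stops taking part from one who wants the data erased. The protocol already keeps some de-identified fields on people who withdraw, so keeping a few more would raise no new principle.

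**Working it through.** **1. The plan's own figure.** Section 3.9.1 wants at least 20 participants after up to 50% attrition: 20 / (1 − 0.5) = 40. This reproduces the planned enrolment.

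**2. What survives deletion.** Arm and timing of withdrawal (before or after allocation) are kept, so the number enrolled stays known. Setting the outcomes against the retained list, for a randomised participant who withdraws on request:

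- 1b, compliance: access status is erased, so the numerator is unknown.
- 1d, baseline part: completeness is erased, so it is unknown.
- 1c, loss to follow-up: someone who withdraws before the follow-up survey is a known non-submitter, so this can still be counted, provided the recorded time of withdrawal shows it. The follow-up part of 1d can be counted in the same way.

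**3. Bounds on compliance.** Let w be the number of withdrawals on request after allocation, and a the number of accessors among the 40 − w who stay. The rate among all 40 lies between a/40 (no withdrawer accessed) and (a + w)/40 (all did). The width is w/40. Neither w nor a is in the documents. The table assumes access near 80% among those who stay.

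| w | a of those who stay | Rate if withdrawers are dropped | Bounds on 40 | Width (points) |
|---|---|---|---|---|
| 1 | 31 of 39 | 79.5% | 77.5% to 80.0% | 2.5 |
| 2 | 30 of 38 | 78.9% | 75.0% to 80.0% | 5 |
| 4 | 29 of 36 | 80.6% | 72.5% to 82.5% | 10 |
| 8 | 26 of 32 | 81.3% | 65.0% to 85.0% | 20 |

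**4. Direction.** If k of the w withdrawers accessed, the true rate is (a + k)/40. Dropping withdrawers gives a/(40 − w), and its error is (w/40) × [a/(40 − w) − k/w]. This is positive only if withdrawers accessed less often than those who stayed. Counting withdrawers as non-accessors gives a/40, with error −k/40, which is never positive. For w = 4 and a = 29:

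| k | True rate | Dropped: 29/36 = 80.6% | Counted as non-accessors: 29/40 = 72.5% |
|---|---|---|---|
| 0 | 72.5% | +8.1 | 0 |
| 1 | 75.0% | +5.6 | −2.5 |
| 2 | 77.5% | +3.1 | −5.0 |
| 3 | 80.0% | +0.6 | −7.5 |
| 4 | 82.5% | −1.9 | −10.0 |

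Errors are in percentage points. The sign depends on the counting rule and on k.

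**5. With the missing field kept.** If access status were retained for withdrawers, k would be known and the bounds would close to a single value on all 40.

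**The case against.** The strongest reply is that the effect is narrow. Silent drop-outs keep their data. People withdrawn for not submitting a baseline survey are never allocated and lie outside 1b. Only explicit requests after allocation count, and the whole study is a descriptive pilot with no significance testing. The retained list is the same in 3.4.5 and 3.8.2, so the rule looks deliberate, and a request to withdraw differs in consent status from simple non-response. All of this stands. It limits the size of the problem but does not explain why access status should be erased when arm and reason for withdrawal are kept.

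A reader might infer more than the documents support:

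- **That reported compliance will be too high.** This needs withdrawers to be dropped from the denominator and to have accessed less than those who stayed. The first is not stated, and 1b is written on enrolled participants. The second is plausible but not shown. For baseline completeness no direction is evident, because everyone enrolled has submitted a baseline survey.
- **That retention can no longer be measured.** Outcome 1c remains countable for those who withdraw before the follow-up survey.
- **That section 3.8.2 contradicts itself**, because it also says that "all original data will be kept for a minimum of 15 years following the publication of results". This reads more naturally as a general rule followed by its exception in the next paragraph.
- **That the Stop/Go recommendation will be distorted.** Section 4.3 bases it on a summary of preliminary analyses, and does not name the compliance rate or set a threshold for it.

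**Conclusion.** The point holds in a limited form. For randomised participants who ask to withdraw, the stated rule makes protocol compliance and baseline completeness unidentifiable, and the loss cannot be undone. Compliance out of 40 is then known only to within w/40: 2.5 points for one withdrawal, 10 for four and 20 for eight. The direction of bias is undetermined.

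This rests on two assumptions. The first is the number of withdrawals on request after allocation, which the documents do not give; if it is zero, nothing is lost. The second is that recruitment reaches 40; section 3.1 also caps recruitment at two months, and with fewer enrolled the same w gives wider bounds. The change is worth making because it is cheap and touches a primary-objective outcome, but the defect does not undermine the pilot.

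**What to change.** Before recruitment:

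- In 3.4.5, 3.8.2 and the plain language statement and consent form, state that data collected up to withdrawal are retained and analysed unless the participant asks for deletion.
- At minimum, add two items to the de-identified fields already retained: whether the allocated resource was accessed (yes/no), and whether the baseline survey was complete.
- State that all randomised participants stay in the denominators of 1b to 1d. Where someone's data have been deleted at their request, report how many such people there are and give the bounds a/40 to (a + w)/40 beside the compliance rate.

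The cost is a few sentences in two protocol sections and the consent form. The one downside is that participants must be told that these de-identified fields are kept after withdrawal. How much more than the two flags may be kept is for the ethics committee to agree.

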3.9. Statistical methods

3.9.1. Sample size estimation

No sample size calculation is required for a pilot study. However, a minimum sample size of at least 20 participants (10 per trial arm) is recommended (40). A sample size of 40 eligible consenting participants will be recruited and enrolled, allowing generously for up to 50% attrition. This inflated sample will ensure that a minimum sample size of N=20 is reached and provide opportunity to assess actual rates of loss to follow-up, protocol compliance and data completeness to inform the main RCT sample size calculation.

3.9.2. Analysis plan

This pilot study is not designed nor powered for testing the significance of change in negative insulin appraisals, strength of association between the intervention, compared to the control, or inferring causality between dependent and independent variables. Using quantitative data, descriptive statistics (frequencies, proportions, measures of central tendency) will be used to explore and describe the feasibility and acceptability of assessment outcomes. A crude estimate for the association between the intervention and ITAS negative scores will be examined using an unadjusted analysis of covariance (ANCOVA). The underlying assumptions of ANCOVA will be assessed where possible: scatter plots for linearity of relationship between baseline and post-intervention ITAS negative score, the Kolmogorov-Smirnov test and normal probability plots for normality of continuous variables and residuals, residual-vs-fitted plots for homoscedasticity of error variance and DFBETA plots for influential observations or outliers.

For the qualitative data, thematic analyses will be used to explore, and identify key themes, from free-text responses about participant's experiences of the resources to inform future developments.

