3.3. Study design

3.3.1. Type of study

The pilot study will use a double-blinded parallel group randomised controlled trial (two-arms, 1:1 ratio) design, comparing a novel psycho-educational insulin therapy web-based resource (intervention) with widely available online text-based information about insulin (control). This design will emulate the planned fully-powered RCT (Stage 3, Section 5). Outcomes will be assessed at baseline and 2-week follow-up.

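### The effect model in 3.9.2 leaves out gender, the randomisation stratum, and is labelled unadjusted although baseline ITAS Negative is evidently its covariate

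*Protocol*

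**What the plan says.** Protocol 3.5.1 (Randomisation and blinding): after the baseline survey, "participants will be allocated to one of two groups, on an equal allocation basis, stratified by gender". Section 3.3.1 describes a "double-blinded parallel group randomised controlled trial (two-arms, 1:1 ratio) design".

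Protocol 3.7 (Outcomes), item 3a, defines the effect outcome: "Mean change in Insulin Treatment Appraisal Scale (ITAS) Negative scores from baseline to follow-up survey, compared to the control arm". The same section says of the pilot that "we do not specify a primary outcome, or set a level of statistical significance for interpreting analyses".

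Protocol 3.9.2 (Analysis plan) gives the one effect analysis: "A crude estimate for the association between the intervention and ITAS negative scores will be examined using an unadjusted analysis of covariance (ANCOVA". It names no covariate. The assumption checks that follow include "scatter plots for linearity of relationship between baseline and post-intervention ITAS negative score". The section opens by stating: "This pilot study is not designed nor powered for testing the significance of change in negative insulin appraisals".

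**The concern.** When allocation is stratified, the usual practice is to carry the stratification factor into the analysis, so that the standard error reflects how participants were randomised. Here the protocol does not merely leave the covariate list open. By calling the estimate crude and the model unadjusted, it fixes a model without gender.

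The label also fits badly with the method. An analysis of covariance adjusts for a covariate by definition, so an unadjusted one cannot be run as worded. The reader has to work out from a diagnostic plot that baseline ITAS Negative is the covariate.

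At stake is the precision and reproducibility of one estimate. Section 3.2.2 makes estimating the likely effect a secondary objective, and section 3.3.1 says that the pilot design emulates the planned full RCT, so a model stated loosely here may be carried forward.

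**Working it through.** **Inputs from the protocol.** 40 randomised 1:1, stratified by gender; minimum of 20 (10 per arm) after up to 50% attrition (3.9.1). The plan's own figure reproduces: 20 / (1 − 0.5) = 40.

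**Assumed inputs.** The protocol gives no SD for ITAS Negative, no baseline to follow-up correlation and no gender difference. Assumed, in units of the baseline SD: baseline SD 1, baseline slope 0.6, residual SD 0.8, two equal gender strata, gender effect γ from 0 to 0.8, random loss.

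**Step 1: which model is meant.** The linearity check sets baseline against post-intervention score, which implies

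follow-up = α + τ·arm + β·baseline + error.

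Subtracting baseline from both sides gives

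change = α + τ·arm + (β − 1)·baseline + error.

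The treatment effect τ is the same in both. In a simulated data set both fits gave 0.3555 with SE 0.1886; only the baseline coefficient moved, from 0.7105 to −0.2895, a difference of exactly 1.

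**Step 2: gender omitted, balance intact (all 40 analysed).** Balanced gender does not add to the true variability of the estimate, but it does enter the residual variance, which becomes about 0.8² + γ²/4. The model SE is therefore too large by roughly the factor √[(0.64 + γ²/4) / 0.64]:

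- γ = 0.5: √(0.7025 / 0.64) = 1.048
- γ = 0.8: √(0.80 / 0.64) = 1.118

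Simulation agrees, with the model SE about 5% and 11% above the true SD. Mean 95% CI widths (6,000 runs per setting, gender balanced within arm):

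| γ | n = 40, without → with gender | n = 20, without → with gender |
|---|---|---|
| 0 | 1.03 → 1.03 | 1.53 → 1.54 |
| 0.2 | 1.04 → 1.03 | 1.55 → 1.54 |
| 0.5 | 1.08 → 1.03 | 1.61 → 1.53 |
| 0.8 | 1.16 → 1.04 | 1.73 → 1.54 |

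The empirical SD of the estimate was practically the same with and without gender (about 0.26 at n = 40, 0.37 at n = 20). The estimate was unbiased in every setting, and coverage without gender was about 95% to 97%.

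**Step 3: gender omitted, half lost at random (40 randomised, 20 analysed).** Stratification protects balance only at randomisation. After random loss, the gender proportion differed between arms by 20 percentage points or more in about 27% of simulated trials. The inflation of the SE then shrinks, and a loss of true precision partly replaces it:

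- γ = 0.8: the SD of the estimate is 0.399 without gender and 0.377 with it, a ratio of 0.399 / 0.377 = 1.06. The model SE without gender is about 3.5% too large.
- γ = 0.5: 0.384 against 0.381, a gain of about 1% from adding gender. The model SE without gender is within about 1% of the true SD.
- γ = 0: 0.370 without and 0.377 with. Adding gender costs 0.377 / 0.370 = 1.02, about 2%.

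**The case against.** The best defence is that nothing hangs on this estimate. The pilot has no primary outcome and no significance level, it states that it is not powered for the comparison, and it labels the estimate crude. Leaving gender out causes no bias, and the error in the SE is on the conservative side. A gender effect of 0.5 to 0.8 SD is large and wholly assumed; at 0.2 SD or less the interval hardly changes, and after heavy attrition a gain worth having appears only near 0.8 SD. All of this stands, and it keeps the severity low.

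It may also be said that covariate lists belong in a statistical analysis plan. That carries less weight here, because the protocol does not leave the list open: it specifies an unadjusted model.

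A reader might go further and infer that 3.9.2 contradicts outcome 3a in 3.7, because one describes an ANCOVA and the other a mean change. The documents do not support that. The linearity check shows that baseline is the covariate, and with baseline in the model the treatment effect is identical for change and for follow-up (Step 1). Comparing ANCOVA with a raw change-score analysis, or quoting the chance of baseline imbalance in ITAS Negative, says nothing against the model that 3.9.2 implies. Nor is the planned Kolmogorov-Smirnov test an error worth raising: normal probability plots that cover the residuals are already in the plan, and the choice between them is a preference.

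**Conclusion.** The point holds at low severity. The protocol stratifies by gender and then specifies an effect model that excludes it, under a label that hides the baseline covariate the model evidently contains. The result is not bias. With all 40 analysed, the SE is about 5% to 11% too large for gender effects of 0.5 to 0.8 SD. With 20 random completers, there is a modest precision loss at 0.8 SD (about 0.40 against 0.38) and next to none at 0.5 SD or less. These sizes depend on the assumed slope, residual SD, gender effect and random loss, none of which the protocol supplies. The case for change rests mainly on matching the analysis to the randomisation and on stating the model unambiguously. The feasibility conclusions, which are the pilot's primary objective, are unaffected.

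**What to change.** In 3.9.2, replace the unadjusted wording with one explicit model: follow-up ITAS Negative score regressed on trial arm, baseline ITAS Negative score and gender, reporting the adjusted mean difference between arms with its 95% CI. In 3.7, word outcome 3a as that baseline-adjusted difference, so that both sections describe the same quantity. If gender is to stay out, 3.9.2 should say so and why, and describe the model as adjusted for baseline only.

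The cost is small. Table 1 shows that gender is collected at screening and ITAS at baseline and follow-up, and the sample size stays at 40. Adding gender uses one degree of freedom and makes the estimate about 2% more variable with 20 analysed if gender turns out not to be prognostic.
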